## **22. Committees**

### **22.1. Safety Monitoring Process**

To promote early detection of safety issues, the Clinical Events Committee (CEC) and Data Monitoring Committee (DMC; see below) will provide evaluations of safety events. Success of this program requires dynamic collection of unmonitored data as soon as the event is reported. This is expedited through the Sponsor or designee, which is responsible for coordinating the collection of information for the subject dossier from the centers and core laboratories. During regularly scheduled monitoring visits, clinical research monitors will support the dynamic reporting process through their review of source document information.

#### **22.1.1. Clinical Events Committee**

A CEC will be used in this study. A CEC is an independent group of individuals with pertinent expertise, including cardiovascular interventional therapy, cardiovascular surgery, and neurology, which reviews and adjudicates important endpoints and relevant adverse events reported by study investigators. The CEC will review a safety event dossier, which may include copies of subject source documents provided by study sites, and adjudicate study endpoint related clinical events. The responsibilities, qualifications, membership, and committee procedures of the CEC are outlined in the CEC charter.

### **22.1.2. Data Monitoring Committee**

The DMC is responsible for the oversight review of all AEs and all SAEs in the roll-in, randomized, Lotus 21 mm Nested Registry cohorts, LOTUS Edge Nested Registry, and the 29 mm LOTUS Edge Valve roll-in and Nested Registry cohorts. The DMC will include leading experts in cardiovascular interventional therapy, cardiovascular surgery, and biostatistics who are not participating in the study and who have no affiliation with BSC. During the course of the study, the DMC will review accumulating safety data to monitor the incidence of CEC events and other trends that would warrant modification or termination of the study. Responsibilities, qualifications, membership, and committee procedures are outlined in the DMC Charter.

### **22.2. Case Review Committee**

A Case Review Committee (CRC) will be comprised of experienced cardiac surgeons and interventional cardiologists, including the Study Coordinating PIs, Center PIs, other Investigators, Proctors and Medical Consultants experienced in TAVR for their clinical/medical expertise, and the Sponsor for technical expertise on the Lotus Valve System requirements. This committee will be responsible for the review of subject screening data to confirm eligibility given the increased surgical risk of the subject population being studied and to ensure consistency of subjects enrolled across study centers. Responsibilities, qualifications, membership, and committee procedures are outlined in the CRC Charter.

### **22.3. Steering Committee**

A Steering Committee consisting of Sponsor Clinical Management, the Study Coordinating PIs, cardiac surgeons, and other investigators experienced in TAVR will be convened. Responsibilities may include oversight of the overall conduct of the study with regard to protocol development, study progress, subject safety, overall data quality and integrity, as well as disseminating any study results through appropriate scientific sessions and publications. Steering Committee members may participate in the review and approval of all requests for data analysis, abstract and manuscript preparation and submission.

## **23. Suspension or Termination**

### **23.1 Premature Termination of the Study**

Boston Scientific Corporation reserves the right to terminate the study at any stage but intends to exercise this right only for valid scientific or administrative reasons and reasons related to protection of subjects. Investigators, associated IRBs/ECs, and regulatory authorities, as applicable, will be notified in writing in the event of study termination.

### **23.1.1 Criteria for Premature Termination of the Study**

Possible reasons for premature study termination include, but are not limited to, the following.

- The occurrence of unanticipated adverse device effects that present a significant or unreasonable risk to subjects enrolled in the study.
- An enrollment rate far below expectation that prejudices the conclusion of the study.
- A decision on the part of BSC to suspend or discontinue development of the device.

### **23.2 Termination of Study Participation by the Investigator or Withdrawal of IRB/EC Approval**

Any investigator or IRB/EC in the REPRISE III study may discontinue participation in the study or withdrawal approval of the study, respectively, with suitable written notice to BSC. Investigators, associated IRBs/ECs, and regulatory authorities, as applicable, will be notified in writing in the event of these occurrences.

### **23.3 Requirements for Documentation and Subject Follow-up**

In the event of premature study termination a written statement as to why the premature termination has occurred will be provided to all participating centers by BSC. The IRB/EC and regulatory authorities, as applicable, will be notified. Detailed information on how enrolled subjects will be managed thereafter will be provided.

In the event an IRB/EC terminates participation in the study, participating investigators, associated IRBs/ECs, and regulatory authorities, as applicable, will be notified in writing. Detailed information on how enrolled subjects will be managed thereafter will be provided by BSC.

In the event an investigator terminates participation in the study, study responsibility will be transferred to a co-investigator, if possible. In the event there are no opportunities to transfer investigator responsibility; detailed information on how enrolled subjects will be managed thereafter will be provided by BSC. The investigator must return all documents and investigational product to BSC, unless this action would jeopardize the rights, safety, or welfare of the subjects.

### **23.4 Criteria for Suspending/Terminating a Study Center**

Boston Scientific Corporation reserves the right to stop the inclusion of subjects at a study center at any time after the study initiation visit if no subjects have been enrolled or if the center has multiple or severe protocol violations/noncompliance without justification and/or fails to follow remedial actions.

In the event of termination of investigator participation, all study devices and testing equipment, as applicable, will be returned to BSC unless this action would jeopardize the rights, safety or well-being of the subjects. The IRB/EC and regulatory authorities, as

applicable, should be notified. All subjects enrolled in the study at the center will continue to be followed per this protocol. The Principal Investigator at the center must make provision for these follow-up visits unless BSC notifies the investigational center otherwise.

## 24. Publication Policy

In accordance with the Global SOP – Human Subject Data and Research Controls, BSC requires disclosure of its involvement as a sponsor or financial supporter in any publication or presentation relating to a BSC study or its results. In accordance with the Global SOP – Human Subject Data and Research Controls, BSC will submit study results for publication (regardless of study outcome) in a timely manner. Boston Scientific Corporation follows authorship principals as set forth in the Uniform Requirements of the International Committee of Medical Journal Editors (ICMJE; <http://www.icmje.org>). In order to ensure the public disclosure of study results in a timely manner, while maintaining an unbiased presentation of study outcomes, BSC personnel may assist authors and investigators in publication preparation provided the following guidelines are followed.

- All authorship and contributorship requirements as described above must be followed.
- BSC involvement in the publication preparation and the BSC Publication Policy should be discussed with the Coordinating Principal Investigator(s) and/or Steering Committee at the onset of the project.
- The First and Senior authors are the primary drivers of decisions regarding publication content, review, approval, and submission.

## 26. Abbreviations and Definitions

### 26.1. Abbreviations

Abbreviations are shown in Table 26.1-1.

**Table 26.1-1: Abbreviations and Acronyms**

Abbreviation/Acronym	Definition
ADE	adverse device effect
AE	adverse event
AKIN	Acute Kidney Injury Network
AR	aortic regurgitation
AS	aortic stenosis
AV	atrioventricular
AVA	aortic valve area
AVR	aortic valve replacement
BARC	Bleeding Academic Research Consortium
BMI	body mass index
BSA	body surface area
BSC	Boston Scientific Corporation

**Table 26.1-1: Abbreviations and Acronyms**

Abbreviation/Acronym	Definition
CBC	complete blood count
CEC	Clinical Events Committee
CK	creatine kinase
CK-MB	creatine kinase-myoglobin band, a fraction of creatine kinase
CRC	Case Review Committee
CT	computed tomography
CVA	cerebrovascular accident
DVI	Doppler velocity index
ECG	Electrocardiogram
eCRF	electronic case report form
EOA	effective orifice area
eGFR	estimated glomerular filtration rate
GCP	Good Clinical Practices
ICF	Informed Consent form
ICH	International Conference on Harmonisation
IEC/IRB	Independent Ethics Committee/Institutional Review Board
IFU	Instructions for Use
ISO	International Organization For Standardization
ITT	intention to treat
LBBB	left bundle branch block
LDH	lactate dehydrogenase
LV	left ventricle
LVEF	left ventricular ejection fraction
MACCE	major adverse cardiovascular and cerebrovascular events
MI	myocardial infarction
MRI	magnetic resonance imaging
mRS	Modified Rankin Scale
NIHSS	National Institutes of Health Stroke Scale
NOAC	new oral anticoagulant
NYHA	New York Heart Association classification
PPM	permanent pacemaker
QOL	quality of life
SADE	serious adverse device effect
SAE	serious adverse event
SAVR	surgical aortic valve replacement
TAVR	transcatheter aortic valve replacement
TEE	transesophageal Doppler echocardiography
TIA	transient ischemic attack
TTE	transthoracic Doppler echocardiography
UADE	unanticipated adverse device effect
USADE	unanticipated serious adverse device effect
URL	upper reference limit (defined as 99 th percentile of normal reference range)

**Table 26.1-1: Abbreviations and Acronyms**

Abbreviation/Acronym	Definition
VARC	Valve Academic Research Consortium

[figure not shown]
**26.2. Definitions**

Terms are defined in Table 26.2-1. See Table 26.1-1 for abbreviations.

**Table 26.2-1: Definitions**

Term	Definition
ACUTE KIDNEY INJURY (AKI) (AKIN System  )	Change in serum creatinine (up to 7 days) compared to baseline: 
 
• Stage 1: Increase in serum creatinine to 150–199% (1.5–1.99 × increase compared with baseline) OR increase of ≥0.3 mg/dl (≥26.4 mmol/L)
 
• Stage 2: Increase in serum creatinine to 200–299% (2.0–2.99 × increase compared with baseline)
 
• Stage 3: Increase in serum creatinine to ≥300% (>3 × increase compared with baseline) OR serum creatinine of ≥4.0 mg/dL (≥354 mmol/L) with an acute increase of at least 0.5 mg/dL (44 mmol/L)
 
 -OR- Based on urine output (up to 7 days): 
 
• Stage 1: <0.5 ml/kg per hour for >6 but <12 hours
 
• Stage 2: <0.5 ml/kg per hour for >12 but <24 hours
 
• Stage 3: <0.3 ml/kg per hour for ≥24 hours or anuria for ≥12 hours
 
 Note 1 : Subjects receiving renal replacement therapy are considered to meet Stage 3 criteria irrespective of other criteria.
ACUTE VESSEL OCCLUSION	The state of complete luminal obstruction with no antegrade blood flow
ADVERSE EVENT Ref: ISO 14155:2011 (AE)	Any untoward medical occurrence, unintended disease or injury or untoward clinical signs (including abnormal laboratory findings) in subjects, users or other persons, whether or not related to the investigational medical device. Note 1 : This definition includes events related to the investigational medical device or the comparator. Note 2 : This definition includes events related to the procedures involved. Note 3 : For users or other persons, this definition is restricted to events related to investigational medical devices.
ADVERSE EVENT BECOME AWARE DATE	The become aware date for an adverse event that requires reporting per the protocol is the date that study personnel listed on the Delegation of Authority Log identify or are notified of the event.
ADVERSE DEVICE EFFECT Ref: ISO 14155:2011 (ADE)	Adverse event related to the use of an investigational medical device Note 1 : This definition includes adverse events resulting from insufficient or inadequate instructions for use, deployment, implantation, installation, or operation, or any malfunction of the investigational medical device. Note 2 : This definition includes any event resulting from use error or from intentional misuse of the investigational medical device.
AORTIC DISSECTION	Intimal tear resulting in blood splitting the aortic media and producing a false lumen that can progress in an antegrade or retrograde direction Aortic dissection is further classified using Stanford classification (Types A and B depending on whether ascending or descending aorta involved) or DeBakey classification (Types

**Table 26.2-1: Definitions**

Term	Definition
	
I, II and III) [see Figure below].
 

AORTIC REGURGITATION (AR)
	
The leaking of the aortic valve that causes blood to flow in the reverse direction during ventricular diastole, from the aorta into the left ventricle.
 
The echocardiographic findings in severe aortic regurgitation include the following.
 
 
• An AR color jet dimension >60% of the left ventricular outflow tract diameter (may not be true if the jet is eccentric)
 
• The pressure half-time of the regurgitant jet is <250 msec
 
• Early termination of the mitral inflow (due to increase in LV pressure due to the AR)
 
• Early diastolic flow reversal in the descending aorta.
 
• Regurgitant volume >60 mL
 
• Regurgitant fraction >55%
 

ARRHYTHMIA
	
Any variation from the normal rhythm of the heartbeat, including sinus arrhythmia, premature beat, heart block, atrial fibrillation, atrial flutter and tachycardia. Complete heart block, ventricular tachycardia and ventricular fibrillation are considered major arrhythmias. Data should be collected on any new arrhythmia resulting in hemodynamic instability or requiring therapy (therapy includes electrical/medical cardioversion or initiation of a new medication [oral anticoagulation, rhythm or rate controlling therapy]).
 
New onset atrial fibrillation or atrial flutter (AF) is diagnosed as any arrhythmia within hospitalization that has the ECG characteristics of AF and lasts sufficiently long to be recorded on a 12-lead ECG, or at least 30 seconds on a rhythm strip.
 
The therapeutic approach to new-onset AF (spontaneous conversion, electrical or medical cardioversion, initiation of oral anticoagulation, and rate or rhythm control medications) and any clinical consequences should be documented.
 
Note 1: See also definitions for conductance disturbance and permanent pacemaker.

AS-TREATED ANALYSIS SET
	
This population includes all subjects who sign an Informed Consent Form, are enrolled in the trial, are randomized, and receive a study device, but subjects are analyzed based on the treatment actually received. For example, if a subject is assigned to receive a test device but instead receives a control device, that subject will be considered a control subject for the as-treated analyses of implant subgroups.

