REPRISE III: REpositionable Percutaneous Replacement of Stenotic Aortic Valve through Implantation of Lotus™ Valve System – Randomized Clinical Evaluation	
	the LOTUS Edge Valve, up to 20 subjects will be enrolled in the LOTUS Edge 29 mm Valve roll-in phase (29 mm valve only; a minimum of 2 roll-in subjects per center) before enrolling in the LOTUS Edge 29 mm Nested Registry.
Primary Endpoints	
Primary Safety Endpoint: Composite of all-cause mortality, stroke, life-threatening and major bleeding events, stage 2 or 3 acute kidney injury, or major vascular complications at 30 days
 
Primary Effectiveness Endpoint: Composite of all-cause mortality, disabling stroke, or moderate or greater paravalvular aortic regurgitation (based on core lab assessment) at 1 year
 
Powered statistical analyses for the primary safety endpoint and the primary effectiveness endpoint will be carried out on the randomized cohort.

Secondary Endpoint	
Moderate or greater paravalvular aortic regurgitation (based on core lab assessment) at 1 year
 
Powered statistical analysis for the secondary endpoint will be carried out on the randomized cohort.

Additional Measurements	
Additional measurements based on the VARCa,b endpoints and definitions (see Note 1 below) will be collected peri- and post-procedure, at discharge or 7 days post-procedure (whichever comes first), 30 days, 6 months, and 1, 2, 3, 4, and 5 years post index procedure, unless otherwise specified below.
 
 
• Safety endpoints adjudicated by an independent Clinical Events Committee (CEC): 
 
○ Mortality: all-cause, cardiovascular, and non-cardiovascular
 
○ Stroke: disabling and non-disabling
 
○ Myocardial infarction (MI): periprocedural (≤72 hours post index procedure) and spontaneous (>72 hours post index procedure)
 
○ Bleeding: life-threatening (or disabling) and major
 
○ Acute kidney injury (≤7 days post index procedure): based on the AKIN System Stage 3 (including renal replacement therapy) or Stage 2
 
○ Major vascular complication
 
○ Repeat procedure for valve-related dysfunction (surgical or interventional therapy)
 
○ Hospitalization for valve-related symptoms or worsening congestive
 
 
 

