## 7.2. Additional Measurements

Additional measurements based on the VARC endpoints and definitions (see **Note 1** below) will be collected peri- and post-procedure, at discharge or 7 days post-procedure (whichever comes first), 30 days, 6 months, and 1, 2, 3, 4, and 5 years post index procedure, unless otherwise specified below.

- Safety endpoints (see **Note 2** below) adjudicated by an independent Clinical Events Committee (CEC; Section 22.1.1):
  - Mortality: all-cause, cardiovascular, and non-cardiovascular
  - Stroke: disabling and non-disabling
  - Myocardial infarction (MI): periprocedural ( $\leq 72$  hours post index procedure) and spontaneous ( $> 72$  hours post index procedure)
  - Bleeding: life-threatening (or disabling) and major
  - Acute kidney injury ( $\leq 7$  days post index procedure): based on the AKIN System Stage 3 (including renal replacement therapy) or Stage 2
  - Major vascular complication
  - Repeat procedure for valve-related dysfunction (surgical or interventional therapy)
  - Hospitalization for valve-related symptoms or worsening CHF (NYHA class III or IV)
  - New permanent pacemaker implantation resulting from new or worsened conduction disturbances (definitions in Table 26.2-1; see **Note 3** below)
  - New onset of atrial fibrillation or atrial flutter
  - Coronary obstruction: periprocedural ( $\leq 72$  hours post index procedure)
  - Ventricular septal perforation: periprocedural ( $\leq 72$  hours post index procedure)
  - Mitral apparatus damage: periprocedural ( $\leq 72$  hours post index procedure)
  - Cardiac tamponade: periprocedural ( $\leq 72$  hours post index procedure)
  - Prosthetic aortic valve malpositioning, including valve migration, valve embolization, or ectopic valve deployment
  - Transcatheter aortic valve (TAV)-in-TAV deployment

- Prosthetic aortic valve thrombosis
- Prosthetic aortic valve endocarditis
- Device performance endpoints peri- and post-procedure:
  - Successful vascular access, delivery and deployment of the study valve and successful retrieval of the delivery system
  - Successful retrieval of the study valve if retrieval is attempted
  - Successful repositioning of the study valve if repositioning is attempted (see **Note 4** below)

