### **12.2.4. Reporting Events**

For all subjects in the roll-in (with the 23 mm, 25 mm, or 27 mm Lotus Valve), Lotus 21 mm Nested Registry, LOTUS Edge Nested Registry, roll-in with the 29 mm LOTUS Edge Valve, LOTUS Edge 29 mm Nested Registry, and U.S. Continued Access Study cohorts, all events that occur from the start of the index procedure will be reported. For all randomized subjects, events from the time of randomization onward will be reported. For randomized subjects who do not have an attempted procedure, events from the date of randomization to 1 year post-randomization will be reported. For time based clinical events, the cut-off for events for 30-day endpoints will be 30 days, for 6-month endpoints will be 180 days, for 1-year endpoints will be 365 days, and for 2-5 year endpoints will be 365 days times the number of years. For events at discharge or 7 days post-procedure, the cut-off for events will be the earlier of the date of discharge or 7 days post-procedure for each subject.

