#### **13.3.3. Electrocardiography (ECG) Core Laboratory**

All 12-lead ECGs performed at each of the required protocol visits will be sent to an ECG core laboratory (see study Manual of Operations) for independent analyses. These analyses will minimize bias and will provide consistent interpretation of the ECGs.

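### New-onset atrial fibrillation is defined as an in-hospital event but listed as an adjudicated endpoint through 5 years, so AF first seen on the 30-day, 6-month and 12-month office ECGs cannot count

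*Combined protocol and SAP*

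**What the plan says.** The Arrhythmia row of Table 26.2-1 gives the only definition of the event: "New onset atrial fibrillation or atrial flutter (AF) is diagnosed as any arrhythmia within hospitalization that has the ECG characteristics of AF", provided that it "lasts sufficiently long to be recorded on a 12-lead ECG, or at least 30 seconds on a rhythm strip".

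Section 7.2 includes "New onset of atrial fibrillation or atrial flutter" in its list of CEC-adjudicated safety endpoints. The list is collected around the procedure, at discharge or 7 days, and at "30 days, 6 months, and 1, 2, 3, 4, and 5 years post index procedure, unless otherwise specified below". Nothing further is specified for AF. Other entries in the same list do carry a limit, for example "Acute kidney injury (≤7 days post index procedure", and several periprocedural events are limited to 72 hours. Section 12.2.4 sets the event cut-offs at 30 and 180 days for the 30-day and 6-month endpoints and then says: "for 1-year endpoints will be 365 days, and for 2-5 year endpoints will be 365 days times the number of years".

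On detection, Table 11.1-1 and Sections 11.10.1 to 11.10.3 require a 12-lead ECG at 30 days, 6 months and 12 months. Section 13.3.3 adds: "All 12-lead ECGs performed at each of the required protocol visits will be sent to an ECG core laboratory". Footnote b of Table 11.1-1 makes these office visits, held in hospital only if the subject happens to be admitted.

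On adjudication, footnote t of Table 11.1-1 and Sections 11.10 and 21.1 all refer to Table 26.2-1 for the CEC event definitions.

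**The concern.** The endpoint list promises an AF rate at each time point to 5 years. The definition that the CEC is told to apply admits AF only if it arises during a hospital stay. The two agree at discharge or 7 days, because that cut-off is the earlier of the two dates and so cannot run past discharge. They part company once the subject has gone home.

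What is at stake is whether a reported number means what its label says. Section 12.1.5 provides estimates by treatment group, differences with 95% confidence intervals, chi-square or Fisher tests, and Kaplan-Meier estimates with log-rank and Wilcoxon comparisons for time-to-event endpoints. A 1-year new-onset AF rate will therefore be shown for each arm, and a reader will take it as AF arising at any time in that year.

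**Working it through.** No sample size, power or alpha figure depends on this definition, so there is nothing to recompute. The check is to take each place where AF could first be recorded and apply the definition literally.

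| Where AF is first recorded | Protocol 12-lead ECG | Meets Table 26.2-1 as written? |
|---|---|---|
| Index stay | Within 24 hours of the procedure, and before discharge or at 7 days (Sections 11.8, 11.9) | Yes |
| Later admission, or a visit held while the subject is admitted | Only if a visit coincides | Yes; the wording does not say index stay |
| 30-day, 6-month or 12-month office visit | Yes, sent to the core laboratory | No |
| Outpatient setting between visits | None | No |
| Office visit at 24 to 60 months | None scheduled | No |

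Four steps follow.

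1. Table 26.2-1 governs, because three places in the protocol send adjudication to it. No other definition of new-onset AF appears, and no text extends it to outpatient detection.
2. Section 7.2 does not restrict AF. Where the authors wanted a short window they wrote one beside the event, and for AF they did not.
3. The third row of the table is the direct conflict. A required ECG, read centrally, can show new AF that the endpoint must then leave out. Three visits are involved, so up to three scheduled ECGs per implanted subject in the first year cannot contribute unless the subject is in hospital at the time.
4. What remains in the 30-day to 5-year rates is AF in the index stay plus AF in subjects who are later admitted. After discharge the rate therefore depends partly on being readmitted.

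The same row of Table 26.2-1 also asks for data on new arrhythmias that cause hemodynamic instability or need therapy. That governs data collection. It does not change which events are diagnosed as new-onset AF, and it would not reach AF that is asymptomatic and untreated.

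**The case against.** The strongest case on the other side is that little is lost. Adverse events are collected through 12 months and their rates reported, so outpatient AF can appear there. The core laboratory analyses the office ECGs in any case. The CEC charter is not part of these documents and may apply the wording more broadly. Section 7.2 says the measurements are based on VARC definitions; if this wording is inherited from there, it has value for comparison with other studies. AF is in neither primary composite nor the secondary endpoint, and Section 12.1.5 plans no inference on additional measurements.

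Most of this stands as a limit on importance. It does not resolve the conflict: an adverse event tabulation is not the adjudicated endpoint, and a broader reading in the charter would contradict the protocol's own table.

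A reader might also infer three stronger things that the documents do not support.

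- That chronic AF would be counted because the definition states no baseline condition. The term defined is new onset, which in ordinary reading excludes it, and the cardiac history and a screening ECG are collected.
- That the REPRISE II counts show the effect: 6 subjects at 30 days and 7 at 1 year in the main cohort (Tables 4.1-2 and 4.1-3), and 16 and 17 in the full cohort (Table 4.1-4). That is another study, its AF definition is not given, and the rates rest on different bases (6/115 against a Kaplan-Meier 6.0%; 16/241 against 17/249). AF that is mainly periprocedural would look equally flat under any definition.
- That the definition biases the comparison because length of stay differs between arms. No figure in the documents shows such a difference, and the definition and ECG schedule are the same in both arms.

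**Conclusion.** The definition and the endpoint list contradict each other, and the contradiction affects what the AF rates after discharge mean. Read literally, AF first detected on an office ECG at 30 days, 6 months or 12 months is not an endpoint event.

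The size is modest. One descriptive safety measure is affected; power, alpha and the success criteria are untouched. The number of AF cases left out cannot be estimated from the documents. Because no protocol ECG is scheduled at 24 to 60 months, the conflict with scheduled ECGs is confined to the three first-year visits.

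The conclusion assumes that the CEC applies Table 26.2-1 as written, as the protocol directs, and that follow-up visits are ordinarily outpatient visits.

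**What to change.** Reconcile Table 26.2-1 with Section 7.2 as follows.

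- Keep the current wording as a separate line labelled in-hospital new-onset AF, and say whether it means the index stay or any admission.
- For the 30-day and later time points, count AF or flutter recorded on any 12-lead ECG, or for at least 30 seconds on a rhythm strip, in any setting after the procedure.
- State that new onset is checked against the medical history and the screening ECG, both already collected.
- State whether an ECG finding is assigned by recording date or by visit. The visit windows run to day 37 (30 + 7), day 210 (180 + 30) and day 395 (365 + 30), past the 30-, 180- and 365-day cut-offs of Section 12.2.4.
- Note beside the 2- to 5-year rates that no protocol ECG is scheduled at those visits, so AF arising after the first year is found only if detected clinically.

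Relabelling the endpoint as in-hospital only would also remove the contradiction, but it would leave unused the follow-up ECGs that are already taken and read.

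The cost is one definition row and a line in the CEC charter, with no new assessments. The any-setting rate may be higher than in earlier studies and less comparable with them; the separate in-hospital line limits that loss.
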